12 HANDLING OF MISSING/INCOMPLETE DATE AND TIME FIELDS

In the following, ‘lower limit’ and ‘upper limit’ refer to the minimum or maximum, respectively, of a possible date. For example, if the day is missing, the lowest limit is the first day of the given month and the upper limit is the last day of the given month. If the day and month are missing, the lower limit refers to the first day of the given year and the upper limit to the last day of the given year. *The earliest and the latest dates refer to the first or last date, respectively, when ordered in sequence.*

12.1 Previous / concomitant therapies

For previous and concomitant therapies with missing or partial start and end dates the following rules for assignment to previous therapies and treatment concomitant therapies are applied [see Table 8].

Table 8 Handling of missing or partial start and end dates for previous/concomitant therapies

eCRF page	Start date	End date	Previous / Concomitant
Prev*	Unless start date clearly after/on STS (Start date either: prior to STS date, partial with either lower or upper limit prior to STS date, or missing)	Unless end date after/on STS (Either prior STS, partial with either lower or upper limit prior STS, or missing)	Previous
Con**	Unless start date clearly after/on STS (as above)	Prior to STS date; or Partial with upper limit prior to STS date;	Previous
Con**	Start date confirmed prior STS (Start date either: prior to STS date, partial with upper limit prior to STS date)	End date on STS date and 'Ongoing at start of Treatment' ticked 'No'; or Partial with lower limit prior to STS date and upper limit after/on STS date and 'Ongoing at start of Treatment' ticked 'No';	Previous
Any	All other cases not listed above for which Start date prior to or on EOT+15 days (Start date either: prior to or on EOT+15 days, or partial with lower limit prior to or on EOT+15 days)	Any	Treatment concomitant
Any	All other cases not listed above for which Start date after EOT+15 days (Start date either: after EOT+15 days, or partial with lower limit after EOT+15 days)	Any	Post-treatment

STS = Study treatment start; For subjects randomized but not treated the randomization date is used instead of the STS.

* Includes 'Previous Medications' or any of the individual MS Specific Treatment History Log eCRFs (e.g., 'Interferon beta-1a history', 'Glatiramer acetate history' etc): On these forms as per CRF completion guidelines only medications that stopped prior to signature of informed consent are to be recorded.

** Includes all forms collecting therapies apart from 'Previous Medications' and any of the individual MS Specific Treatment History Log eCRFs.

Subjects randomized but not treated are not considered to have any treatment concomitant medications.

To further flag treatment concomitant therapies as 'ongoing at study treatment start' or 'started during study drug administration' medications the following rules apply:

- Study concomitant therapies with missing start date or partial start dates potentially falling into the treatment period (i.e., lower limit prior or on EOT) are considered to have been started during study drug administration unless 'Ongoing at start of Treatment' ticked 'Yes' then it is considered ongoing at study treatment start.

12.1.1 Previous / concomitant therapies date imputation

The following imputation of partial dates is made:

Previous therapies: Impute partial start date with lower limit, and partial end date with minimum of upper limit and study treatment start date – 1. Missing dates are not imputed.

Treatment concomitant therapies ongoing at study treatment start: Impute partial start date with lower limit and partial end date with upper limit. Missing dates are not imputed.

Treatment concomitant therapies not ongoing at study treatment start: Impute partial start date with maximum of lower limit and study treatment start date, impute partial end date with upper limit. Missing dates are not imputed.

12.2 Relapse

Type of date/time	Date/time is incomplete	Date/time is missing
Relapse start date (collected on 'Relapse Summary' eCRF)	Maximum of lower limit and randomization date Unless upper limit is prior to randomization date, then upper limit	Randomization date

eCRF = electronic case report form.

12.3 Adverse event onset and death dates

The following imputation rules are applied for (partially missing) AE onset dates and (partially missing) dates of death:

- Onset day missing: If month and year is clearly on or after study treatment start (short: STS, the date of first study drug intake) month and year, and clearly before or on the month and year of last intake date + 15 days, consider the event as treatment-emergent. With regard to the date imputation, the following rules are applied:
 - If the record's origin is the First-Dose eCRF and month and year correspond to month and year of STS, impute onset date and time as the date and time of the first study drug intake.
 - If the record's origin is the First-Dose eCRF and month and year are clearly after STS month and year, but a date of re-initiation with corresponding month and year is documented, impute onset date and time as the date and time of this re-initiation study drug intake (in case more than one study drug re-initiations are documented in this month and year, impute with the date and time of the earliest of those).
 - If the record's origin is the First-Dose eCRF and month and year are clearly after STS month and year, but no date of re-initiation with corresponding month and year is documented, the onset date is imputed to the 1st day of the month and year given and time to 00:00.

- If the record’s origin is the main CRF and month and year is clearly on or after STS month and year, the onset date is imputed as the maximum of (date of Treatment Day 2, 1st day of the month and year given) and time is imputed to 00:00.
- If event onset month and year is clearly prior to the STS month and year, the onset date is imputed to the last day of the given month (i.e., 28th, 29th, 30th, or 31st depending on month) and year and time is imputed to 00:00. This imputation is done irrespective of eCRF origin (First-Dose or Main).
- Onset day and month missing: If the year is the same year as the year of STS or later, and if the year is prior to or in the same year as the last intake date + 15 days, consider AE as treatment-emergent. With regard to the date imputation, the following rules are applied:
 - If the record’s origin is the First-Dose eCRF and the year corresponds to the year of STS, impute onset date and time as the date and time of the STS.
 - If the record’s origin is the First-Dose eCRF and the year is clearly after the year of STS, but a date of re-initiation with corresponding year is documented, impute onset date and time as the date and time of this re-initiation study drug intake (in case more than one study drug re-initiations are documented in this year, impute with the date and time of the earliest of those).
 - If the record’s origin is the First-Dose eCRF and the year is clearly after the year of STS, but no date of re-initiation with corresponding year is documented, the onset date is imputed to January 1st of the given year and time to 00:00.
 - If the record’s origin is the main CRF and year is clearly on or after the year of STS, the onset date is imputed as date of maximum of (Treatment Day 2, January 1st of the given year) and time is imputed to 00:00.
 - If the event onset year is clearly prior to the year of STS, the onset date is imputed to 31-December of the given year and time is imputed to 00:00. This imputation is done irrespective of eCRF origin (First-Dose or Main).
- Missing onset time is imputed to
 - the time of the STS, if the onset date equals the STS.
 - the time of the study drug intake at re-initiation, if the onset date equals the date of a documented study drug re-initiation.
 - 00:00, for any other onset date.
- Onset date is completely missing: Consider as treatment-emergent.
The onset date and time is imputed as date and time of the STS (if death date or if AE onset date with record’s origin is the First-Dose eCRF), if AE onset date with record origin in the main CRF, the onset date is imputed as Study Day 2.

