A safety assessment (ECG, vital signs, laboratory) is considered treatment-emergent, if the assessment date is on or after the study treatment start date and prior to or on the study treatment end date + 15 days (inclusive). If both, the assessment date/time and the date/time of study treatment start are available, only events with date/time on or after the date/time of study treatment start are considered to be treatment-emergent. In case of (partially) missing assessment dates/times, or for assessments on treatment Day 1 with reported assessment time contradicting the timepoint label, the nominal visit and timepoint labels will be used to determine whether an assessment is considered as treatment-emergent or not. For example, a blood pressure measurement with an assessment date on Day 1 but a missing assessment time or an assessment time after the time of first study drug intake, will not be considered treatment-emergent if reported under the timepoint “Pre-dose” in the eCRF, however it will be considered if reported as “2 hours post-dose” in the eCRF.

A safety event (AE, serious AE [SAE], Death) is considered treatment-emergent if the onset date/date of occurrence is on or after the study treatment start date and prior to or on the EOT date + 15 days (inclusive). Missing or partially missing onset or occurrence dates are imputed as described in Section 12.3. If both the onset/occurrence date/time and the date/time of study treatment start are available, only events with date/time on or after the date/time of study treatment start are considered to be treatment-emergent.

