9.9 Analysis of safety variables

9.9.1 Adverse events

All AEs captured (i.e., from signature of informed consent up to EOS) are reported in the subject listings based on the SCR, treatment-emergent events are flagged.

Unless otherwise specified, the SAF is used for all analyses of AEs.

An overview of treatment-emergent AEs is presented, per treatment group, as the number and percentage of subjects having any AE, any severe AE, any drug-related AE, any AE leading to study drug discontinuation, any SAE, any drug-related SAE, or any fatal SAE.

Also, AEs are summarized by SOC and PT: Presenting, per treatment group, the number and percentage of subjects having any AE, having an AE in each primary SOC, and having each individual AE (PT). SOC's are sorted by descending order of frequency in the ponesimod arm. If the frequencies of SOC's are the same, alphabetical order is used. The same rule applies for PT's within SOC. The following summaries are presented:

- Treatment-emergent AEs
- Treatment-emergent AEs on Day 1
- Treatment-emergent AEs on Day 1 of re-initiation, for subjects with at least one re-initiation
- Treatment-emergent AEs leading to temporary interruption of study treatment
- Treatment-emergent AEs considered to be related to DMF
- Treatment-emergent AEs considered to be related to study drug
- Treatment-emergent AEs with fatal outcome

Also, treatment-emergent AEs are summarized by PT: presenting, per treatment group, the number and percentage of subjects having any AE, and having each individual AE (PT). PT's are sorted by descending order of frequency in the ponesimod arm. If the frequencies are the same, alphabetical order is used.

For the disclosure of the results to EudraCT and ClinicalTrials.gov (and inclusion in the CSR appendix), frequent treatment-emergent non-serious AEs, i.e., PT's reported in $\geq 5\%$ of subjects in at least one treatment group, are summarized as follows:

- 1) The number and percentage of subjects having any frequent non-serious AE, and having each individual non-serious AE (PT).
- 2) The overall number of frequent non-serious AEs (i.e., reported episodes), and the number and percentage of frequent AEs (PT). Here the denominator is the overall number of frequent non-serious AEs.

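### Section 12.3 imputes AE onset and treatment-emergent status without the AE end date, so an event that ended before the first dose can be counted as treatment-emergent

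*SAP*

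**What the plan says.** Section 5.5.1 defines a treatment-emergent event by its onset alone: on or after study treatment start and no later than end of treatment + 15 days. For incomplete dates it defers to Section 12.3: "Missing or partially missing onset or occurrence dates are imputed as described in Section 12.3".

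For main-CRF records, Section 12.3 then sets both the status and the date:

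- **Day missing.** If the onset month is the month of study treatment start or later, and "clearly before or on the month and year of last intake date + 15 days, consider the event as treatment-emergent". For the date, "the onset date is imputed as the maximum of (date of Treatment Day 2, 1st day of the month and year given").
- **Day and month missing.** The status rule begins "If the year is the same year as the year of STS or later", with an upper bound at the year of last intake + 15 days. For the date, "the onset date is imputed as date of maximum of (Treatment Day 2, January 1st of the given year").
- **Nothing known.** "Onset date is completely missing: Consider as treatment-emergent". The date becomes Study Day 2.

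If the known month or year is clearly before treatment start, the onset goes to the last day of that month or year and the event is not treatment-emergent. No branch refers to the AE end date.

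Events before dosing are in the data. Section 9.9.1 states: "All AEs captured (i.e., from signature of informed consent up to EOS) are reported in the subject listings". Section 2.1.1 allows a pre-randomization period of up to 45 days per screening attempt.

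**The concern.** An AE cannot start after it has ended. If a recorded end date precedes the first dose, the event was not treatment-emergent, whatever is missing from its onset date. Section 12.3 discards that information and can produce a record whose onset lies after its resolution.

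At stake is the accuracy of the treatment-emergent AE, SAE and AESI counts in Sections 9.9.1, 9.9.2.2 and 9.9.2.4.1, together with onset-after-end records in the analysis data and listings. No efficacy result is touched.

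**Working it through.** The SAP gives no figure to reproduce, so the check applies the main-CRF rules literally to example dates. The dates are illustrative: study treatment start (STS) 20 May 2019, so Treatment Day 2 is 21 May 2019.

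| Recorded onset | Recorded end | Rule | Imputed onset | Days after own end | Treatment-emergent |
|---|---|---|---|---|---|
| May 2019, day missing | 12 May 2019 | max(21 May, 1 May) | 21 May 2019 | 9 | Yes |
| 2019, day and month missing | 25 Apr 2019 | max(21 May, 1 Jan) | 21 May 2019 | 26 | Yes |
| April 2019, day missing | 25 Apr 2019 | last day of month | 30 Apr 2019 | 5 | No |

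The first two rows are false treatment-emergent events. The third has an impossible date, but its status is right.

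Re-running the first two rows with onset = min(imputed onset, end date) gives 12 May and 25 April. Both precede STS, so neither is treatment-emergent.

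**Which part of screening is exposed.** Assume a full 45-day screening period, AE onsets spread evenly over it, and first doses spread evenly over a 365-day year.

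- *Day missing.* The mean number of days in the start month that precede the start date is [7 × (31 × 30/2) + 4 × (30 × 29/2) + 28 × 27/2] / 365 = (3255 + 1740 + 378) / 365 = 14.7. As a share of screening days, 14.7/45 = 33%. With a 30-day screening period it would be 14.7/30 = 49%.
- *Day and month missing.* Screening days falling in the previous calendar year total 45 + 44 + … + 1 = 1035, out of 365 × 45 = 16,425. The share falling in the start year is 1 − 1035/16,425 = 94%.

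These are shares of pre-treatment AEs that already have the stated gap in the onset date. They are not shares of all pre-treatment AEs, and among the exposed events only those that also ended before STS are provably misclassified.

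**What one record can do.** Section 1 gives 136 subjects. Assuming 68 per arm, one subject is 1/68 = 1.5%. Section 9.9.1 selects frequent non-serious preferred terms at 5% or more in either arm: 3/68 = 4.4% and 4/68 = 5.9%. One misdated event can therefore bring a term into that table.

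**How the SAP treats similar dates.** In Section 5.4.2.1, a relapse start with the day missing is limited by the relapse end date when deciding which EDSS assessments to set aside. In Table 8 (Section 12.1), a therapy that is not clearly started on or after STS, and whose end date or the upper limit of a partial end date precedes STS, is classed as previous.

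**The case against.** The best defence is that Section 12.3 follows a deliberate worst-case policy. Missing severity becomes severe (5.5.2.2), missing relationship becomes related (5.5.2.3 and 5.5.2.4), missing seriousness becomes serious (5.5.4), and a morphological ECG finding without an evaluable pre-treatment ECG counts as new (5.5.11.2). That policy is sound and should stay wherever the timing is uncertain. It does not cover an event with a recorded end before the first dose, where the status is known.

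Other objections stand, at least in part:

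- The analogy with Table 8 is imperfect. A previous therapy is defined as one both started and stopped before treatment (5.2.3.1), so its end date belongs to the definition, whereas treatment-emergence rests on onset. Section 12.2 also imputes relapse start without an end date. The relapse rule in 5.4.2.1 is the closer precedent.
- The SAP does not show that the AE eCRF holds an end date.
- All AEs are listed with treatment-emergent flags, so an affected record could be noticed.
- A plain cap at the end date has a side effect. A main-CRF event ending on the start date would move from Day 2 to Day 1, its missing time would become the time of first dose, and it would enter the Day 1 table defined in 5.5.8.

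A reader might also infer more than the SAP supports:

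- *That a pile-up on Day 2 distorts the up-titration safety picture.* The planned AE summaries cover the whole treatment-emergent period, Day 1, and Day 1 of re-initiation. None is by time to onset or by titration phase.
- *That the treatment contrast is diluted or biased.* AE output is counts and percentages with no test, and extra events expected equally in both arms leave the expected difference roughly unchanged.
- *That a third of pre-treatment AEs become treatment-emergent, or that the end date would settle nearly all of them.* The 33% applies only to those with the day missing, under the assumptions shown. An event still ongoing at first dose stays ambiguous even with a known end date.

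**Conclusion.** The gap is real as written. For main-CRF events whose partial onset falls in the month of treatment start (or in the year, if the month is also missing), or whose onset is wholly missing, Section 12.3 can count as treatment-emergent an event that its own record shows was over before the first dose.

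The size is limited. It needs an incomplete onset, a recorded end date, and resolution before dosing. How many records meet all three cannot be determined from the SAP; it is probably few and could be none. The likely effect is a few false entries in descriptive AE, SAE or AESI tables and some onset-after-end records, by the same rule in both arms. The change is still worth making because the rule gives a logically impossible result and the correction is small. The conclusion assumes that the AE eCRF records an end date.

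**What to change.** Amend Section 12.3 as follows:

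1. **New first step.** If the AE end date, or the upper limit of a partial end date, is before the study treatment start date, the AE is not treatment-emergent and its imputed onset is no later than its end date.
2. **AE ending on or after study treatment start.** Keep the present treatment-emergent status and limit the imputed onset date to the end date. State that a main-CRF AE moved to the start date only by this limit is not counted in the Day 1 tables.
3. **End date missing or event ongoing.** Keep the present rules unchanged.

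The cost is a few sentences in the SAP and one extra condition in the AE derivation program, plus confirmation that the AE eCRF holds an end date. No new data collection is needed if it does.

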12.4 Study treatment start and EOT

The following imputations of study treatment start and EOT are considered for assigning safety events and assessments to the treatment-emergent period and used for deriving efficacy variables with definitions requiring EOT date. It is not considered for derivation of exposure variables.

Details for assigning safety events and assessments to the treatment-emergent period, as described in Section 5.5.1, apply.

Type of date/time	Date/time is incomplete	Date/time is missing
Study treatment start date	Maximum of lower limit and randomization date.	Randomization date
Study treatment start time	See missing.	0:00 or randomization time if study treatment start date (after imputation) is equal to randomization date.
EOT	Earliest between treatment start date + 1092 days (156 weeks), the upper limit, EOS date, and Death date.	Earliest between treatment start date + 1092 days (156 weeks), EOS date and Death date.

EOS = End of Study; EOT = End of Trial.

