Subjects who prematurely discontinue study drug and complete the 30-day safety follow-up including the FU visit, will enter the PTOP which lasts until 60 weeks after randomization of the last subject or until Week 156, whichever is first (i.e., planned EOT visit) irrespective of treatment completion. The PTOP consists of an abbreviated schedule of assessments at the time of the originally scheduled 12-weekly visits (i.e., not all assessments are performed, see visit schedule). Safety follow-up visits are conducted in addition, following the post-treatment safety follow-up period schedule.

- **End-of-study:** the study level EOS occurs after all subjects have completed the safety follow-up period or the last visit of the PTOp. For an individual subject, EOS is reached when treatment, post-treatment safety follow-up, and if applicable, the PTOps have been completed:
 - For subjects who complete the treatment period, and for subjects who prematurely discontinue study treatment and do not enter the PTOp, the EOS visit corresponds to the 30-day follow-up visit (FU visit).
 - For subjects who prematurely discontinue study treatment and enter the PTOp period, the EOS visit corresponds to the last visit of the PTOp.

Table 1 **Dosing scheme**

Treatment period	Duration	Dose regimen in the ponesimod group
Titration	Day 1 and 2	2 mg
Titration	Day 3 and 4	3 mg
Titration	Day 5 and 6	4 mg
Titration	Day 7	5 mg
Titration	Day 8	6 mg
Titration	Day 9	7 mg
Titration	Day 10	8 mg
Titration	Day 11	9 mg
Titration	Day 12 to 14*	10 mg
Maintenance	Day 15 until EOT	20 mg

- * Visit 4 is to take place at Day 15 ± 1 day.
- EOT = End-of-Treatment.

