5.1.5 Subject study treatment completion status

Due to the early termination of the study, no treatment completers as per protocol are expected as no subjects will have completed 156 weeks of treatment / 60 weeks of treatment following randomization of the last subject.

Subjects who complete study treatment up to study termination are defined as those meeting any of the following conditions:

- a record in the eCRF ‘Maintenance Ponesimod/Placebo’ form with reason for treatment end given as ‘Completed as per protocol’;
- reason ‘Sponsor decision’ with sub-reason ‘Study termination’ (for question ‘Study treatment stopped due to’) is reported on the eCRF form ‘Premature Discontinuation of Study Treatment’,
- the reason for treatment end is documented as ‘Study Closure Announcement by Sponsor’ on the eCRF ‘Up-titration Ponesimod/Placebo’ or ‘Maintenance Ponesimod/ Placebo’.

A subject is considered to have prematurely discontinued from the study treatment if:

- at least one reason (‘Study treatment stopped due to’) which is not ‘Sponsor decision’ with sub-reason ‘Study termination’ is reported on the eCRF form ‘Premature Discontinuation of Study Treatment’ and/or
- the reason for treatment end is documented as ‘Premature Permanent Discontinuation’ on the eCRF ‘Up-titration Ponesimod/Placebo’ or ‘Maintenance Ponesimod/ Placebo’.

The date of treatment discontinuation is the last date study drug was taken [defined in Section 5.3.1.1]. In case of a (partially) missing discontinuation date, the date is imputed with the EOS date as defined in Section 5.1.6, or with the upper limit of the partial date if prior to EOS.

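### A completely missing end-of-treatment date is imputed with the end-of-study date, so for subjects in the post-treatment observation period off-drug data become treatment-emergent

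*SAP*

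**What the plan says.** Section 12.4 has two rules for EOT. A completely missing date becomes "Earliest between treatment start date + 1092 days (156 weeks), EOS date and Death date". An incomplete date becomes "Earliest between treatment start date + 1092 days (156 weeks), the upper limit, EOS date, and Death date". The imputed date is "considered for assigning safety events and assessments to the treatment-emergent period" and also serves efficacy variables whose definition needs EOT. On exposure the section is explicit: "It is not considered for derivation of exposure variables".

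Section 5.1.5 has a similar rule for the treatment discontinuation date: "In case of a (partially) missing discontinuation date, the date is imputed with the EOS date as defined in Section 5.1.6", or the upper limit of a partial date if that is earlier.

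Section 2.1.1 fixes what EOS means for the subjects at issue: "For subjects who prematurely discontinue study treatment and enter the PTOp period, the EOS visit corresponds to the last visit of the PTOp". Section 5.1.6 sets the EOS date from the reason for leaving the study. For subjects followed until the sponsor's termination, it is the last recorded visit or assessment.

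Section 5.5.1 ends the treatment-emergent period 15 days after EOT. Sections 2.1 and 2.1.1 admit to the PTOP only subjects who have stopped study drug and completed the 30-day safety follow-up with its FU visit.

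**The concern.** Every PTOP day is off study drug by design. An EOT date placed at the end of the PTOP therefore cannot be the last dose, and the subject's visit record already shows this. Two scheduled visits bound the last dose much more closely: the premature EOT visit (Visit 18, window +7 days) and the FU visit (last dose + 30 days, window +7 days). Section 12.4 uses neither.

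There are data to misassign. Table 4 schedules laboratory tests, lymphocytes and blood pressure at all PTOP visits, ECG and spirometry at some, and adverse events throughout. Section 11.4 tabulates nominal visits whether or not they took place in the PTOP. For ECG, vital signs, laboratory and spirometry, the restriction to treatment-emergent results in Sections 9.9.3 to 9.9.6 is what keeps off-drug PTOP values out of the by-visit tables. A late imputed EOT removes that safeguard for the subject concerned.

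**Working it through.** **Inputs.** Imputation rule and 156-week cap: Section 12.4. Treatment-emergent end at EOT + 15 days: Section 5.5.1. First enrolment in March 2017 and termination decision on 26 November 2019: Section 1. Last PTOP visit (18A) within 4 weeks: Section 2. Visit windows: Table 3. The stop and EOS days below are assumptions.

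**The plan's own figure.** 156 × 7 = 1092 days, as stated.

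**Does the 1092-day cap help?** Take the earliest possible treatment start, 1 March 2017, and count the 4 weeks from the decision date (both assumptions).
- Cap date: 1 March 2017 + 1092 days = 26 February 2020.
- Latest PTOP visit: 26 November 2019 + 28 days = 24 December 2019, which is 1028 days after the start.
- With a start on 31 March 2017 the figure is 998 days.

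Both are below 1092, so for a living PTOP subject the earliest of the three dates is the EOS date.

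**Size for a completely missing date.** Imputed EOT = min(1092, EOS day). The correct window ends at last dose + 15. No study data follow EOS, so observed days misclassified = EOS day − (last dose day + 15).

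| Last dose (day) | EOS (day) | Imputed EOT late by | Observed days misclassified |
|---|---|---|---|
| 168 | 336 | 168 | 336 − 183 = 153 |
| 336 | 672 | 336 | 672 − 351 = 321 |
| 168 | 672 | 504 | 672 − 183 = 489 |
| 84 | 1028 | 944 | 1028 − 99 = 929 |

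In the third row, days 184 to 672 are misclassified: 489/672 = 73% of follow-up. For a subject who does not enter the PTOP, EOS is the FU visit at 30 to 37 days, and only 15 to 22 observed days are misclassified.

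**Effect on outputs for one such subject.**
- Any-event adverse event counts, lymphocyte nadir and worst-case abnormality flags: the longer window can only add to them.
- By-visit means: PTOP results enter as treatment-emergent.
- Last on-treatment value (latest up to EOT + 1 day): becomes the final PTOP value where the parameter is measured then.
- Day-30 follow-up (EOT + 16 to EOT + 37 days): moves past EOS, so it is empty.
- On-treatment EDSS flag (before EOT + 7 days, Section 5.4.4.2): set for off-drug assessments.
- Post-treatment safety set (EOS later than EOT + 15 days, Section 7.1.4.1): with EOT equal to EOS the condition fails, if the imputed date is used there.

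**The case against.** The trigger is narrow. Section 5.3.1.1 takes EOT as the latest end date on any study drug log, and sites had to reconcile intake with the eDiary and returned tablets. Read literally, a completely missing EOT needs a subject with no recorded end date at all. The long overshoot further needs that subject to have entered the PTOP, among 136 randomized. This stands, and it limits the point.

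The rule also resembles the SAP's other cautious defaults: missing severity counts as severe, missing relationship as related, and missing onset as treatment-emergent. That defence holds for any-event counts and extremes. It does not hold for means, last on-treatment values, the follow-up window or EDSS flags, where off-drug data are not cautious.

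Four stronger readings are tempting, and the documents do not support them.
- A reader might infer that adverse event or nadir results are diluted. These count subjects with any event, or take the extreme, so added time can only inflate them.
- A reader might infer that partial dates suffer the same error. With only the day missing, the upper limit holds the overshoot to about 30 days. With the month also missing it can approach a year, still bounded by EOS.
- A reader might count all 504 days of delay in the 168/672 example as misclassified data. The observed figure is 489.
- A reader might expect Section 5.1.5 to distort disposition tables. Section 9.3.1 tabulates reasons, and no output is named that uses the imputed date.

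The adverse event part is also less certain than the rest. A footnote to Table 3 requires reporting only to 30 days after discontinuation, while Table 4 lists adverse events at PTOP visits.

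**Conclusion.** The rule gives a demonstrably wrong date for a living PTOP subject with a completely missing EOT, and nothing elsewhere in the SAP bounds it. In the assumed cases, 153 to 929 observed off-drug days would be treated as treatment-emergent. How many subjects are affected is not stated and may be zero, so this is a worthwhile tightening and not a threat to the study's conclusions. Duration and compliance are untouched, because Section 12.4 excludes exposure variables. The conclusion that EOS is the operative term rests on the March 2017 start and on counting the 4 weeks from the decision date. The SAP gives the start only to the month.

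**What to change.** In both EOT columns of Section 12.4, add to the list of candidate dates the date of the premature EOT visit (Visit 18) or, if that visit was not done, the FU visit date. Align the discontinuation-date rule in Section 5.1.5 for consistency. State whether the imputed date is used for the post-treatment safety set.

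The cost is one extra term in the derivation and no new data. Some overshoot remains: about 7 days if the EOT visit was on time, or 30 to 37 days if only the FU visit is available. The protocol deviation code list foresees EOT visits that are late or not done, so the fallback is needed. It will not normally improve a date missing only its day, which the upper limit already bounds about as tightly. For a completely missing date in a subject who did not enter the PTOP, it adds nothing, since EOS is already the FU visit.
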